Micronutrients and Pregnancy Outcomes HIV-uninfected Women: In the PeriNatal Study, a double-blind trial in Dar es Salaam, Tanzania, we randomly assigned 8,468 HIV-uninfected pregnant women (gestational age of fetus, 12 to 27 weeks) to receive daily multivitamins (including multiples of the recommended dietary allowance) or placebo. All the women received prenatal supplemental iron and folic acid and malaria prophylaxis. Multivitamin supplements significantly reduced the risk of low birth weight by 18%, decreased the risk of small for gestational age by 23%, and reduced the risk of maternal anemia (hemoglobin level, <11 g/dL; relative risk, 0.88; 95% CI, 0.80 to 0.97; P=0.01),but had no significant effects on fetal loss or prematurity [144].

Zinc and Perinatal Outcomes: Poor zinc status has been associated with adverse pregnancy outcomes, but higher levels of zinc intake were significantly associated with higher risks of mortality among US men. We examined the effects of zinc supplementation on pregnancy outcomes and hematologic and T cell counts of HIV-infected women in Dar es Salaam (n=400). Retention rates were high at 95%. Zinc supplements had no effect on pregnancy outcomes or CD4, CD8, or CD3 cell counts during the follow-up period. However, zinc had an adverse effect on hemoglobin, red blood cell count, and packed cell volume. The rise in hemoglobin over this period was significantly lower (P = 0.03) in the zinc group (x +/- SD: 11.5 +/- 17.9 g/L) than in the placebo group (15.2 +/- 18.6 g/L); similarly, the changes in red blood cell count and in packed

cell volume over the same period were significantly lower in the zinc group (P < 0.01 and P = 0.01, respectively) [145]. These adverse effects may be due to adverse effect on iron absorption, as previously observed in other studies.

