
Experimental Regimens and Randomization Procedures: Women will be randomly assigned to receive a daily oral dose of one of the following two regimens from enrollment and until delivery: (a) 60 mg iron (as ferrous sulphate) or (b) placebo. Tablets will be packaged in identical coded bottles that contain supply for 45 days (although the research visits are scheduled at monthly intervals, the extra tablets are necessary in case a woman is delayed in coming in for her scheduled visit). A list from 1 to 1500 will be prepared according to a randomization sequence in blocks of 20. Each of the two study clinics where randomization will occur will have a subset of the list of numbers. At enrollment, each eligible woman will be assigned to the next numbered bottle of regimen at that site. Experience has shown that unblinding, whether real or based on an impression or perception that develops among subjects or staff, is more likely to occur if regimens are color-coded or bear simple numeric codes. To minimize this risk, we will provide the regimen in bottles labeled with the participant's identification numbers, and will make active tablets and placebo indistinguishable, so that neither the subjects nor the investigators can identify which group of subjects is randomized to the same regimen.

The proposed dose of 60 mg elemental iron (200 μ g ferrous sulphate) is the WHO-recommended dose for universal supplementation during pregnancy. It also corresponds to the WHO-recommended dose for daily supplementation over a 3-month period among lactating women and women of reproductive age who live in areas where the prevalence of anemia exceeds 40% [84]. Although the prevalence of anemia among women of reproductive age exceeds 40% in Tanzania [33], the WHO-guidelines during lactation and reproductive age have not been adopted by the Tanzanian Ministry of Health and this practice is thus currently not in use [84].

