Modification of any treatment effects observed by a third variable, such as gravidity or maternal mid-upper arm circumference, will be explored by stratification and testing for significance of the difference between the treatment effects observed in two strata. For effect modifiers which are continuous or have more than two levels, the logistic regression model will be used to quantify effect modification and test for statistical significance, through the creation of model interaction terms and use of the likelihood ratio test to assess significance. Since there are no *a priori* effect modifiers hypothesized, our study is not designed to detect any which may occur, and we acknowledge that unless there is strong modification of an observed treatment effect, the power of our study to detect these will be quite low.

Placental malaria, defined as a continuous variable of parasite density will be compared between the two treatment arms. The difference in these measurements for the two treatment groups, and the statistical significance of any difference observed will be assessed by a two-sample t-test and non-parametrically by the Wilcoxon rank-sum test. Linear regression models will be used to evaluate effect modification, such as by baseline iron status, or dietary intake by creating appropriate cross-product terms and evaluating their significance by F-tests. To evaluate treatment-related differences in change after adjusting for risk factors which remained imbalanced after randomization, linear regression models of the change variables on treatment status and other risk factors will be used.

Hemoglobin: This parameter will be assessed three times (at baseline, 30 weeks of pregnancy and at delivery). In the primary analyses we will compare the mean change between baseline and delivery. This change will be calculated as the average within-women difference in these measurements for the two treatment groups, and the statistical significance of any difference observed will be assessed by a two-sample t-test and non-parametrically by the Wilcoxon rank-sum test. Linear regression models will be used to evaluate hemoglobin levels between the treatment arms, adjusting for factors that were imbalanced after randomization, and effect modification.

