Power for the primary aims, placental malaria infection and density, maternal hemoglobin levels, and birth weight, have been calculated based on a nominal Type I error rate (alpha) of 0.05, and a 10% sample size adjustment for loss-to-follow-up and fetal loss. Power is based on a 2-sided test of proportions, based on a Z-statistic using the asymptotic variances of the observed proportions. The table below displays the power of the study to detect treatment effects on placental malaria infection. The assumed placebo arm rate of 20-30% is supported by studies reviewed above [37, 39]. Displayed is the power (for treatment effects expressed as % reductions) based on a 2-sided test for comparison of proportions, total enrolled n=1500, with a 10% sample size adjustment to account for loss to follow-up and fetal loss.

Statistical Power for Incidence of Placental Malaria							
Incidence in Placebo Arm	Effect of Intervention on the Incidence						
	HR=0.75	HR=0.70	HR=0.65	HR=0.60			
20%	48%	65%	80%	90%			
25%	57%	74%	87%	95%			
30%	64%	80%	92%	98%			

The study will have good power to detect a 35% effect size, for placental malaria rates as low as 20% in the placebo arm. If the placental malaria rates are larger (25% or 30%), the study will have good power to detect a 30% effect size and excellent power to detect a 40% effect size.

Continuous Variables: The table below displays the power of the study to detect treatment effects on continuous variables, including placental malaria density, maternal hemoglobin concentration, and birth weight. Displayed is the power (for treatment effects expressed as percent changes in effect size) based on a 2-sided test for comparison of proportions, total enrolled n=1500, with a 10% sample size adjustment to account for loss to follow-up.

Placental malaria density: The table below displays the power of the study to detect treatment effects on placental malaria density. The assumed mean placental malaria density in the placebo arm of 9,000 parasites/ μ L is supported by studies reviewed above [156]. The study will have good power to detect an effect size of 8.5%, and excellent power to detect a 10-20% change, based on a 2-sided test for comparison of proportions, total enrolled n=1500, with a 10% sample size adjustment to account for loss to follow-up and fetal loss. The study will have good power to detect an 8.5% effect size, and excellent power to detect an effect size of 10% or greater.

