Maternal hemoglobin concentrations: The table below displays the power of the study to detect treatment effects on maternal hemoglobin concentrations. The assumed mean hemoglobin levels in the placebo arm of 11.4 g/dL is supported by studies reviewed above [157]. The study will have good power to detect a 5% effect size, and excellent power to detect a 10% change or greater.

Statistical Power for Continuous Variables							
Variable	Mean	SD	Minimal	Power for	Power for	Power for	Power for
(Units)			effect size	5% change	10%	15%	20%
			for 80%		change	change	change
			power				
Placental	9000	5000	8.5%	38%	91%	>99%	>99%
malaria							
density							
(parasites/µL)							
Maternal	11.4	3.8	5.0%	79%	>99%	>99%	>99%
hemoglobin							
concentration							
(g/dL)							
Mean birth	3083	400	2.0%	>99%	>99%	>99%	>99%

weight				
(grams)				

Birth weight: The table above displays the power of the study to detect treatment effects on birth weight. The assumed mean birth weight in the placebo arm of 3,083 grams is supported by studies reviewed above [144]. The study will have good power to detect a 2% effect size, and excellent power to detect a 5% change or greater.

Data Safety Monitoring Board (DSMB)

We have constituted a DSMB to oversee another maternal health study, and we will ask this board to oversee the proposed study as well. Members of the DSMB provide varied and complementary expertise and include: [name] (clinician, infectious diseases, Tanzania), [name] (nutrition, epidemiology, clinical trials, Denmark), [name] (epidemiology, malaria, Tanzania), and [name] (Biostatistics, clinical trials, USA). [name] (nutrition, epidemiology, USA) will serve as the chair of the board. DSMB members will not be paid.

It is anticipated that the first review will occur before the initiation of the study, with subsequent reviews biannually thereafter. Each meeting will include an administrative review to assess accrual, retention, and the progress of the study. In addition, the DSMB will monitor the occurrence of any adverse effects; these will include clinical signs and results of laboratory investigations done within the context of the trial. The DSMB will define stopping and unblinding rules at its first meeting. Additional reviews or an altered schedule may be instituted at the discretion of the DSMB.

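### The primary haemoglobin test is an unadjusted change score, less efficient than baseline-adjusted regression, and its power row rests on an unsourced SD of 3.8 g/dL that is not tied to the variable tested

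*Protocol*

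**What the plan says.** The Hemoglobin paragraph under Data Analysis (Protocol) fixes the primary comparison: "In the primary analyses we will compare the mean change between baseline and delivery". The change is the average within-woman difference in each arm, and the "statistical significance of any difference observed will be assessed by a two-sample t-test and non-parametrically by the Wilcoxon rank-sum test". A regression follows: "Linear regression models will be used to evaluate hemoglobin levels between the treatment arms, adjusting for factors that were imbalanced after randomization". Baseline haemoglobin is one of the variables listed for the imbalance check in the Placental Malaria Infection paragraph, so it can enter that model, but only if the check selects it.

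Under Statistical Power Calculations, the maternal haemoglobin row gives a placebo-arm mean concentration of 11.4 g/dL, SD 3.8 g/dL, a minimal effect of 5.0% for 80% power, and 79% power for a 5% change. The text concludes: "The study will have good power to detect a 5% effect size, and excellent power to detect a 10% change or greater". A reference supports the mean; none is given for the SD.

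The only SDs of haemoglobin change in the protocol are in Preliminary Studies, Zinc and Perinatal Outcomes, where the rise was lower "in the zinc group (x +/- SD: 11.5 +/- 17.9 g/L) than in the placebo group (15.2 +/- 18.6 g/L").

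**The concern.** There are two separate matters.

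- **Efficiency.** Every woman has a baseline and a delivery haemogram. Subtracting the baseline value forces its coefficient to be 1, whereas regression estimates it. Adjusting only when an imbalance turns up loses most of the benefit, because the gain comes from the correlation between baseline and delivery values, whether or not the arms happen to differ at baseline. Precision matters here. The trial enrols women who are not iron deficient, and the Introduction itself expects little response to iron in those with haemoglobin between 8.5 and 11.0 g/dL, so a small effect is plausible.
- **Planning SD.** The power row describes a concentration, but the planned test is on a change. The two have the same SD only under a particular correlation, and the protocol does not say which of them 3.8 g/dL is meant to be. The stated detectable effect therefore cannot be tied to the analysis that will be run.

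**Working it through.** **Inputs.** Type I error and loss: "nominal Type I error rate (alpha) of 0.05, and a 10% sample size adjustment for loss-to-follow-up and fetal loss". Size: "based on a 2-sided test for comparison of proportions, total enrolled n=1500, with a 10% sample size adjustment to account for loss to follow-up". That wording speaks of proportions, but the haemoglobin figures reproduce as a comparison of two means. Evaluable women: 1500 × 0.9 = 1350. The allocation ratio is not stated ("A list from 1 to 1500 will be prepared according to a randomization sequence in blocks of 20"); 1:1 is assumed, giving 675 per arm.

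**1. The protocol's own figures.** SE = 3.8 × √(2/675) = 0.207 g/dL.

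- Detectable difference at 80% power: (1.960 + 0.842) × 0.207 = 0.579 g/dL, and 0.579/11.4 = 5.08% (stated 5.0%).
- Power for 5% (0.57 g/dL): Φ(0.57/0.207 − 1.960) = 78.7% (stated 79%).

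Both reproduce.

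**2. Change score against baseline-adjusted regression.** Let s0 and s1 be the baseline and delivery SDs and r their correlation.

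- Variance of change: s0² + s1² − 2·r·s0·s1
- Residual variance after regression on baseline: s1²(1 − r²)
- Difference: (s0 − r·s1)², which is never negative

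So in large samples with 1:1 allocation the regression is never less precise. With s0 = s1 the ratio of the two variances is 2/(1 + r). The extra women that the change score needs for the same precision are:

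| Assumed r | s0 = s1 | s0 = 0.8·s1 |
|---|---|---|
| 0.3 | 2/1.3 = 1.54: 54% | 1.16/0.91 = 1.27: 27% |
| 0.5 | 2/1.5 = 1.33: 33% | 0.84/0.75 = 1.12: 12% |
| 0.7 | 2/1.7 = 1.18: 18% | 0.52/0.51 = 1.02: 2% |

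The second column matters because entry requires haemoglobin of at least 8.5 g/dL. That truncates baseline values but not delivery values, so a smaller baseline SD is plausible. The figure 0.8 is an assumption.

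**3. If 3.8 g/dL is the SD of a level** (equal SDs assumed), the SD of change is 3.8 × √(2(1 − r)):

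| Assumed r | SD of change (g/dL) | Power for 5%, change score | Power for 5%, adjusted regression |
|---|---|---|---|
| 0.3 | 4.50 | 64% | 82% |
| 0.5 | 3.80 | 79% | 89% |
| 0.7 | 2.94 | 94% | 97% |

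The stated 79% belongs to the planned test only at r = 0.5.

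**4. If 3.8 g/dL is the SD of change,** compare it with the zinc-trial values of 17.9 and 18.6 g/L, that is 1.79 and 1.86 g/dL: 3.8/1.79 = 2.12 and 3.8/1.86 = 2.04. With those SDs:

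- 2.802 × 1.79 × √(2/675) = 0.27 g/dL (2.4% of 11.4)
- 2.802 × 1.86 × √(2/675) = 0.28 g/dL (2.5%)

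Power for a 5% effect would exceed 99%. With a change SD of 1.86 g/dL and equal baseline and delivery SDs, adjusted regression would lower the detectable difference further, to 0.23, 0.25 or 0.26 g/dL at r = 0.3, 0.5 or 0.7.

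**The case against.** The change-score t-test is valid and unbiased under randomisation, so this is a gain in efficiency and not the repair of an error. That stands. The protocol also has a regression that may include baseline haemoglobin. That stands too, though a covariate chosen by an imbalance check is weaker than one fixed in advance.

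The size of the gain is uncertain. It depends on a correlation that the protocol does not give and on the ratio of the SDs; in the least favourable case shown it is 2%. If the SD of change really is near 1.8 g/dL, power is already ample and the gain amounts to a few hundredths of a g/dL. This is a fair limit on the practical weight of the point.

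The zinc-trial SDs come from HIV-infected women followed over a period whose length is not stated, whereas this trial enrols HIV-uninfected women within limits on haemoglobin and ferritin. They show that 3.8 g/dL needs a justification; they do not establish the right value. Similarly, a normal distribution with mean 11.4 and SD 3.8 g/dL would put 22% of women below 8.5 g/dL, but the entry limit applies at screening and the power row gives no time point, so this makes 3.8 look doubtful without refuting it.

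A reader might infer that an inflated planning SD would mislead about what a null result rules out. It would not: the observed confidence interval determines that, and it uses the observed SD.

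**Conclusion.** The point holds as two modest, separate faults. First, the primary haemoglobin analysis is valid but less efficient than a prespecified baseline-adjusted regression. The cost is 18% to 54% more women for r between 0.7 and 0.3 with equal SDs, falling to about 2% to 27% if the baseline SD is 0.8 of the delivery SD. The values of r, the SD ratio and 1:1 allocation are all assumptions. Second, the SD of 3.8 g/dL has no source and is not tied to the change that is tested. As a level SD it matches the stated power only at r = 0.5; as a change SD it is about twice the only such figures in the protocol.

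It may be tempting to say that the 5.0% detectable effect is wrong, or that haemoglobin is underpowered. The documents support neither as a general statement. The row reproduces from its own inputs, so the doubt is about an input and not the arithmetic. On the zinc-trial SDs the error is conservative and the sample size is not threatened. Only the reading as a level SD with a correlation below 0.5 would put power for a 5% effect under the stated 79%, and nothing in the protocol establishes that case.

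**What to change.** - Make the primary haemoglobin analysis a linear regression of delivery haemoglobin on arm and baseline haemoglobin, with baseline haemoglobin fixed in advance whatever the imbalance check shows. Report the adjusted mean difference with its 95% CI.
- Keep the t-test and Wilcoxon test on change as sensitivity analyses.
- In the power section, state which variable the SD describes, give its source, and use an SD that matches the primary analysis. If the zinc-trial figures are used, say that they come from HIV-infected women and show a range around them.
- Restate the detectable effect in g/dL as well as in per cent.

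The cost is wording in the protocol, and in the analysis plan if there is one. Baseline and delivery haemograms are already scheduled for all women, so no data collection or sample size changes.

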2. To determine the **efficacy** of iron supplementation among pregnant Tanzanian women, on the **incidence of low birth weight,** compared to placebo.

3. To determine the **efficacy** of iron supplementation among pregnant Tanzanian women, on the **incidence of maternal malaria infection,** compared to placebo.

4. To determine the **efficacy** of iron supplementation among pregnant women on **infant hemoglobin concentrations at 6 weeks**, compared to placebo.

5. To determine the **efficacy** of iron supplementation among pregnant Tanzanian women on **infant malaria parasitemia at 6 weeks**, compared to placebo.

6. To determine the **adherence** to iron supplementation intake by pregnant women compared to placebo.

Background and Significance

Burden of Iron Deficiency

Iron deficiency is the most common form of anemia worldwide; approximately 50% of anemia is attributable to iron deficiency [16-18]. Iron deficiency has a detrimental impact on human health, nutrition, and socioeconomic development. Globally, iron deficiency accounts for 841,000 deaths and 35,057,000 disability-adjusted life years lost, and ranks ninth globally among the 26 leading risk factors worldwide [19]. Pregnant women are particularly vulnerable to iron deficiency and anemia, and anemia is the most common medical disorder in pregnancy. Approximately 41.8% of pregnant women (56 million) are anemic worldwide [1], with iron deficiency anemia accounting for the majority of cases. Anemia has been related to increased maternal morbidity and mortality and adverse perinatal outcomes [20-27] and reduced cognitive development and functioning [28-30] and work capacity [30, 31]. Iron deficiency anemia is a severe public health problem in malaria-endemic countries of Africa. Approximately 17.2 million pregnant women and 83.5 million children under five are anemic in sub-Saharan Africa [1]. Iron deficiency contributes to 22% of all maternal mortality (30-44 years), and 33% of all perinatal mortality [32].

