Hemoglobin: Hemoglobin is the most commonly used diagnostic indicator for anemia, due to its low cost and feasibility. According to the World Health Organization, anemia is defined as hemoglobin levels below 11 g/dl for pregnant women, and less than 12 g/dl for non-pregnant women [3]. In Tanzania and other countries in sub-Saharan Africa, 8.5 g/dl is conventionally used as a cut-off for anemia. However, hemoglobin does not reflect iron stores, and varies due to physiological changes such as hemodilution. For example, low hemoglobin concentrations at the end of the second trimester are considered normal and even beneficial because they signify appropriate plasma volume expansion (hemodilution), unless the mean corpuscular volume is reduced [76]. Both hemoglobin and hematocrit have low sensitivity and are not as informative as other methods of iron status assessment. These methods are, however, simple and inexpensive to perform and feasible in resource-poor settings. Iron stores, hemodilution, and inflammation are important factors to consider when interpreting hemoglobin values in the context of pregnancy.

Serum Ferritin: Serum ferritin is an excellent indicator of iron status of populations [72]. The WHO Consultation considered serum ferritin to be the best indicator of total body iron stores, depleted iron stores, defined as 12 μ g/L (approximately 100 mg of storage iron) [71]. Although a higher cut-off of 30 μ g/l has been proposed for iron deficiency assessment in the presence of infection for children under five [77] and pregnancy [74,78], few studies have examined this cut-off in pregnant women in developing countries. The cutoff of SF<12 has been used to define iron deficiency in several studies among HIV-uninfected pregnant women in sub-Saharan Africa [79-83]. As an acute phase protein, serum ferritin concentrations increase in response to inflammation, even if iron stores are low [72]. Therefore, in settings with high infectious disease burden, the measurement of an indicator of inflammation can further interpretability of serum ferritin as a marker of iron stores. Utilization of an acute phase protein may improve the interpretability and utility of serum ferritin as an indicator of iron status. Serum ferritin cutoffs have also been proposed for iron overload among men (>200 μ g/l,>300 μ g/l) [84, 85] and women (>150 μ g/l, >200 μ g/l) [84-86].

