Adherence: Any trial requires a high degree of adherence in taking the experimental regimens since non-adherence can bias the results of the trial and decrease the statistical power of a study to detect any true effects. We will encourage each woman to take her regimen at the same time every day, to put the bottle in a visible place, and to ask a relative to remind her to take the regimen. During each monthly visit, adherence with supplement use will be assessed in three ways: (a) Direct questioning: asking the woman about her ingestion of the capsules in the previous 24 hours, previous week and previous month. (b) Capsule count: the number of capsules remaining in each monthly bottle will be counted. (c) Biochemical assessment: assessment of adherence biochemically is more accurate as a method of assessment, provided there is a reasonable biochemical marker. We intend to assess the subjects' adherence with use of the experimental regimen by measuring the concentration of serum ferritin. A blood specimen will be collected at randomization and at delivery for this purpose from a sample of 300 randomly selected women. Research assistants will define lack of adherence as any deviation from complete adherence defined using pill count. At all visits, they will assess the patient's adherence with treatment, identify potential barriers to adherence, and identify solutions to these obstacles.

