approximately one fourth of the distance from the center to the edge of the placenta [154]. The specimens will be fixed in 10% neutral buffered formalin and processed for routine paraffin embedding. Paraffin sections ($5 \mu m$ thick) will be stained with haematoxylin and eosin (H&E), Giemsa's stain, and the periodic acid-Schiff technique. Sections will be examined by light microscopy and under polarized light for the presence of malaria pigment and parasitized erythrocytes. The presence of parasites in maternal erythrocytes in intervillous spaces and fetal erythrocytes in fetal stem vessels will be assessed, and, when present, the percentage of parasitized erythrocytes will be estimated. Malaria pigment will be assessed semi-quantitatively (0 = absent; 1 = mild; 2 = abundant) in maternal and fetal parts of the placenta.

Routine examination of urine and stool (i.e. macroscopic and microscopic assessment including presence and burden of parasites) will be done at baseline. On a subset of 300 individuals, iron markers will be measured at randomization and delivery to assess patients' adherence with the use of the regimen and to ascertain the impact of iron supplementation on these indicators. Retinol binding protein and zinc will be measured in order to examine potential interactions between iron and vitamin A and zinc. An extra 5 ml of blood will be drawn from participants in the sub-sampe for these tests. **The above-mentioned laboratory tests will be performed at the Department of Pathology at MUHAS, Muhimbili-Harvard Laboratory in Dar es Salaam**. All laboratory staff, including the pathologist who reads the placental histopathology slides, will be blinded to the mother's randomization group and to any treatments for malaria.

Hemoglobin: Hemoglobin will be measured as part of a complete blood count, measured using a CBC5 Coulter Counter (Coulter Corp. Miami, FL). Sickle cell anemia will be diagnosed using a hemoglobin electrophoresis test.

Serum Ferritin: Ferritin will be measured by a particle-enhanced immunoturbidimetric assay using the Hitachi 917 analyzer (Roche Diagnostics, Indianapolis, IN) and Kamiya Biomedical reagents (Seattle, WA). The reference range for serum ferritin is 15 to 200 mcg/L for women.

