Birth Weight: The difference between mean birth weights in the iron and placebo arms will be calculated, and the statistical significance of any observed difference will be assessed by a two-sample t-test and non-parametrically by a Wilcoxon rank-sum test. A linear regression model will be used to adjust for residual treatment imbalances by risk factors, and to evaluate effect modification by these risk factors, using the methods for multivariate modeling described above.

Analysis of Secondary Endpoints

Low Birth Weight (<2500 g): Analyses of the effects of iron supplements on low birth weight will parallel those outlined above for placental malaria infection, also a binary endpoint.

Maternal anemia (Hb < 11.0 g/dL) and Maternal malaria infection: These binary secondary endpoints, as noted in the Definition of Endpoints section, will be analyzed in a similar fashion as the primary endpoints as described above, although only women without these conditions at baseline will contribute to these analyses.

Analysis of Adherence and Iron Status Biomarkers: Pill counts will be undertaken at monthly clinic visits. Serum concentrations of ferritin will be assessed on all subjects at baseline and among a subset of 300 women at delivery. Increased intake of iron is usually paralleled by increases in serum ferritin values, and concentrations of serum ferritin and pill counts will be compared between the active treatment and placebo arms as proxy indicators for adherence with the supplements. The analysis will be based on a regression model for the change from baseline to delivery and supplemented by Wilcoxon rank-sum tests. Median changes (and associated order-statistic-based 95% CI's) will be summarized by treatment arm. The effect of iron supplementation on serum transferrin receptor, hepcidin, and C-reactive protein will be also examined, following a similar approach.

Statistical Power Calculations

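### A between-arm comparison of serum ferritin cannot answer the adherence aim, because only one arm receives iron

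*Protocol*

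**What the plan says.** Secondary aim 6 (Specific Aims) is to determine adherence "to iron supplementation intake by pregnant women compared to placebo", which is a between-arm question. The section on experimental regimens gives the two arms as "a) 60 mg iron (as ferrous sulphate) or (b) placebo".

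The Adherence section lists three methods: direct questioning, capsule count and a biochemical measure. The last is to be done "by measuring the concentration of serum ferritin" in 300 randomly selected women. That section regards biochemical assessment as the more accurate method if a reasonable marker exists. It also has research assistants define lack of adherence from the pill count.

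Under Analysis of Adherence and Iron Status Biomarkers, the protocol notes that "Increased intake of iron is usually paralleled by increases in serum ferritin values". It then says that "concentrations of serum ferritin and pill counts will be compared between the active treatment and placebo arms as proxy indicators for adherence". The method is a regression on change from baseline to delivery, with Wilcoxon rank-sum tests. Ferritin is taken in all women at baseline and "among a subset of 300 women at delivery".

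Laboratory Investigations gives the iron markers in the same 300 women a second purpose, to "ascertain the impact of iron supplementation on these indicators". The background section on serum ferritin adds: "As an acute phase protein, serum ferritin concentrations increase in response to inflammation, even if iron stores are low".

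**The concern.** A marker can compare adherence between two arms only if it responds to tablet-taking in both. Ferritin responds to the iron tablet and not to the placebo. A fully adherent and a wholly non-adherent placebo arm would be expected to show the same ferritin. The arm difference therefore combines how much iron was taken with how strongly iron moves ferritin, and it contains nothing about placebo-taking.

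At stake is the reading of a named secondary aim. If the ferritin contrast is taken literally as an adherence comparison, a difference would suggest better adherence on iron even where both arms took their tablets equally well. The protocol gives no rule for the case where ferritin and pill counts disagree, and its remark on the accuracy of biochemical assessment could lead a reader to prefer ferritin.

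**Working it through.** The protocol gives no power, SD or expected effect for the ferritin comparison, so there is no stated figure to reproduce. The check is first a matter of logic, then an illustration of size.

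**Logic, from the protocol's own statements**

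1. Iron intake raises ferritin (analysis section).
2. Only one arm receives study iron (regimens section).
3. So, at equal adherence in both arms, the expected ferritin change still differs by the effect of the iron taken.
4. The same measurements are also meant to show the impact of iron (Laboratory Investigations). One contrast cannot separate that impact from an adherence difference between arms.

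**Inputs for the illustration**

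- Women per arm: 300 / 2 = 150. The 300 is from the analysis section; the equal split is an assumption. Laboratory Investigations and the test schedule list delivery ferritin without the subset limit. The analysis section's figure is used here.
- Two-sided alpha 0.05. The protocol states this for the primary aims; it is assumed here.
- Iron effect on ferritin change, d, in SD units: assumed 0.2, 0.3 and 0.5.
- True adherence: identical in both arms.

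**Formula:** probability of a significant difference ≈ Φ(d × √(n/2) − 1.96), with √(150/2) = 8.660.

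| d (SD) | d × 8.660 | minus 1.96 | Probability |
|---|---|---|---|
| 0.2 | 1.732 | −0.228 | 41% |
| 0.3 | 2.598 | 0.638 | 74% |
| 0.5 | 4.330 | 2.370 | 99% |

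**Simulation check** (3,000 runs, 150 per arm, the same adherence distribution in both arms with mean 90%, inflammation in 25% of each arm adding 0.5 SD). The ferritin t-test was significant in 5.6% of runs with no iron effect, 70.9% at 0.3 SD and 98.6% at 0.5 SD. In the runs with inflammation balanced at 25%, a direct adherence measure, such as an accurate pill count, differed between arms in 4.7% to 6.0% of runs, about the nominal rate. The small shortfall from 74% to 71% arises mainly because inflammation adds variance.

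**Inflammation.** With 25% inflamed in both arms and no iron effect, the mean ferritin difference was 0.001 SD, so there was no bias. If iron itself raised inflammation from 25% to 40% and had no direct effect on ferritin, the shift was 0.08 SD (expected 0.5 × 0.15 = 0.075) and about 11% of runs were significant. The prevalences and the 0.5 SD are assumptions.

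**The case against.** The strongest defence is that the analysis section does not say a ferritin difference will be reported as an adherence difference. Because it opens by noting that ferritin follows iron intake, it can be read as a group-level exposure check: if the iron arm took its tablets and the placebo arm took little outside iron, ferritin should separate. On that reading the probabilities above are the power of a useful check, not an error rate. This reading is fair, and ferritin is valid for that purpose. But the section describes the comparison as one of adherence, and aim 6 asks for an arm comparison, so the wording does not settle which reading applies.

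It is also true that non-adherence is already defined by pill count, that recall is collected as well, and that the effect on iron markers is already planned as an outcome. Most of the remedy is therefore in place.

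A reader might infer several stronger points that the documents do not support:

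- That the plan is certain to report a false adherence difference. This depends on an effect size that the protocol does not give; at 0.2 SD the test would miss the difference more often than not.
- That iron raises ferritin whatever the adherence. Untaken tablets raise nothing, which is why ferritin does carry adherence information within the iron arm.
- That inflammation invalidates the contrast. Randomisation balances inflammation unless iron changes it. CRP is also to be compared by arm in the same section, so a difference would be visible.
- That the planned adjustment for non-adherence (Limitations) is compromised. The protocol does not say which measure that adjustment will use.

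**Conclusion.** The point holds in a limited form. The between-arm ferritin comparison cannot answer aim 6, because ferritin is uninformative about tablet-taking in the placebo arm. This conclusion follows from the protocol's own statements and needs no assumed effect size.

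How often equal adherence would still produce a significant ferritin difference does rest on assumptions: 41%, 74% and 99% for iron effects of 0.2, 0.3 and 0.5 SD, with 150 women per arm and two-sided alpha of 0.05.

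Only the ferritin part of the adherence comparison is affected; pill counts and recall remain usable in both arms. Inflammation is a side issue that matters only if iron alters it. Severity is minor: one secondary aim is exposed to misreading, and no primary endpoint, safety comparison or sample size depends on it.

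**What to change.** Reword the analysis section in three respects:

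1. Answer aim 6 by comparing pill counts and recall between arms, and not ferritin.
2. Report the between-arm ferritin change as an effect on iron status, or as a group-level check that the arms differed in iron exposure.
3. Use ferritin as an adherence marker only within the iron arm, by relating its change to pill count.

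A CRP-adjusted ferritin estimate may be added as an optional sensitivity analysis beside the unadjusted one. It should not replace it, because CRP at delivery is measured after randomisation and could itself be affected by iron.

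The cost is a few sentences. All the data needed are already planned, and no visit, sample or sample size changes.
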